- 3. *POC testing for UTI.* Women will be asked about symptoms typically associated with UTIs; their urine will be tested by urinalysis strip if symptoms are reported; and treatment will be given as appropriate.
- 4. *POC testing for vaginal infections regardless of symptoms*. All women regardless of symptoms will be offered vaginal pH measurement with litmus paper attached to a vaginal swab to diagnose BV, POC testing for TV, and treatment for BV and/or TV as appropriate. They will also be asked about symptoms typically associated with vaginal candidiasis, and treatment based on symptom-reporting. In addition, all women will be counselled about safer sex, cessation of harmful vaginal hygiene practices, and male penile hygiene, to minimise BV recurrence.
- 5. POC testing for other curable STIs (syphilis, NG and CT) if pregnant or considered at risk by risk scoring questionnaire. The questionnaire will be developed in the beginning of the project using the behavioural factors that were most strongly associated with these curable STIs in previous RU studies. If considered at high risk by risk scoring questionnaire or pregnant, POC testing will be conducted, and treatment given as appropriate.
- 6. Treatment of genital ulcers/inguinal bubos and lower abdominal pain according to the syndromic management guidelines.
- 7. Partner notification and treatment, if applicable.
- 8. *Referrals to antenatal, HIV, family planning and other care, if applicable.*

In addition to offering these services, research activities will be carried out as follows:

- 1. To monitor and evaluate the services offered, we will collect data on monitoring and evaluation (M&E) indicators. Data for most M&E indicators will be available as part of routine clinic procedures (such as numbers of women counselled and risk scored, diagnostic tests conducted, infections diagnosed and treated, referrals made, etc.) but others will require interviewing participants at the end of their visit (client satisfaction survey), interviewing staff at the end of the study (about their experiences providing the services), timing of procedures done by different staff members, and timing of client trajectories.
- 2. To evaluate the performance of POC tests for NG, CT and TV compared to providing syndromic management alone, we will ask all women at the beginning of their visit (before any POC tests

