1.4 STI syndromic management: WHO and Rwandan guidelines

The WHO published its STI syndromic management guidelines¹ in 2003 to allow for diagnosis and treatment of STIs in resource-poor settings where laboratory testing is not available and physical examination skills are scarce. The original idea was that each symptom syndrome (vaginal discharge syndrome (VDS), lower abdominal pain (LAP), genital ulcer disease (GUD), etc) would be treated for

¹ World Health Organization, 2003: Guidelines for the Management of Sexually Transmitted Infections.

all organisms that might cause the syndrome. This was later expanded by the addition of physical examinations (if available), and the possibility to tailor the guidelines to local STI epidemics as well as person-centered risk assessments. A next version of the guidelines was published in 2008² but the VDS and LAP algorithms for women were unaltered. Flowcharts of the WHO algorithms relevant for the WISH study are shown in appendix 8.1.

The Rwandan STI management guidelines were published in 2010³ with an update in 2013⁴ (see appendix 8.2). Only the treatment guidelines, but not the diagnostic algorithms, were revised in this update. The Rwandan STI management guidelines differ substantially from the WHO guidelines:

- Both guidelines contain two different VDS algorithms: one with and one without a speculum and bimanual examination (and the WHO guidelines also incorporate the possibility of local wet mount or Gram stain microscopy). However, the Rwandan guidelines assume that the clinician can distinguish between mucopurulent cervical discharge and/or cervicitis (which is to be treated for CT/NG/TV) and non-mucopurulent vaginal discharge (which is to be treated for BV/TV/candidiasis). We believe that speculum examinations will rarely be available, and when available, will mostly be used to identify PID, GUD, buboes, condylomata, and other visible/palpable pathologies, but cannot be reliably used to distinguish between different types of discharge. In this SAP, we will therefore only use the VDS algorithms in the absence of a speculum and bimanual examination when evaluating algorithm performances.

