All women were risk-scored for CT/NG and syphilis. Each of the two risk scores consisted of four questions based on the face-to-face interview and findings during speculum and bimanual examination (if applicable). GeneXpert CT/NG testing was only offered if the participant was positive for the CT/NG risk score and syphilis testing was only offered if the participant was positive for the syphilis risk score. However, a sample for GeneXpert testing was taken from all participants (a vaginal sample with the option of a urine sample if the participant refused vaginal sampling) so that we would have a CT/NG GeneXpert result for all participants at the end of the study. Participants who had a negative CT/NG risk-score but tested positive on the GeneXpert later on in the study were contacted for treatment at an Additional Visit.

CT/NG risk score	n (%) N = 705
Currently pregnant	
Exchanged sex for money or goods in the past 12 months	
New sex partner in the past three months	
Abnormal cervicovaginal discharge during speculum exam and/or cervical motion/adnexal tenderness during bimanual exam (if pelvic/bimanual not done, the answer was no)	
Final CT/NG risk score ¹ : - Positive	
- Negative	
Syphilis risk score	n (%)
Currently pregnant	
Exchanged sex for money or goods in the past 12 months	
New sex partner in the past three months	
Genital ulcers/blisters/sores visible during pelvic exam (if pelvic/bimanual not done, the	
answer was no)	
Final syphilis risk score ¹ : - Positive	
- Negative	

Abbreviations: CT = *Chlamydia trachomatis*; NG = *Neisseria gonorrhoeae*.

1. The risk score was positive if at least one of the four criteria was positive. If a speculum/bimanual examination was not done, the answer was no for that question.

Urogenital symptoms reported spontaneously and after structured questioning at Main Visits: During the face-to-face interview, participants were asked the following two questions in the order given:

- "Do you experience, or did you experience in the past 2 weeks, any urogenital symptoms?" We

will refer to these as *spontaneously reported symptoms*.

- "Do you experience, or did you experience in the past 2 weeks, any of the urogenital symptoms below?", followed by a list of symptoms that were read out loud to the participant. We will refer to these as *structurally reported symptoms*.

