Pelvic, bimanual and physical examinations performed at Main and Additional Visits: At the Main Visit, speculum and bimanual examinations were only performed if the participant reported relevant and moderate/severe urogenital symptoms. If she only had UTI-related symptoms (burning when passing urine, frequent urination or urge to urine, or blood in urine), a speculum and bimanual examination was not offered, and UTI testing and treatment were offered based on symptom-reporting. In the case of candidiasis-related symptoms (curdlike unusual vaginal discharge and genital itching), a speculum and bimanual examination was done at the discretion of the study physician; the protocol allowed the study physician to treat the participant based on the reported symptoms alone. If a pelvic and bimanual examination was performed, and no signs of vaginal candidiasis were seen, no treatment for vaginal candidiasis was given.

During Additional Visits, a pelvic and bimanual examinations were only performed if the participant had not had an examination at the Main Visit (for example, because she was menstruating), or if her symptoms had not resolved after having received treatment.

Speculum, bimanual, and physical examinations	MV n (%)	AV n (%)
	N = 705	N = 705
N women who underwent a speculum exam	•	
Reason for speculum exam ⁺ :	N = XXX	N = XXX
- To evaluate symptoms		
- At the participant's request		
- Another reason, specify [additional categories to be made if needed]	••	
Any abnormalities observed by physician during speculum exam	N = xxx	N = xxx
If yes, which one(s) ¹ :	N = xxx	N = xxx
- Enlarged/tender inguinal lymph nodes		
- Abnormal (genital) odour		
- Warts or condylomata (any location genitalia)		
- Ulcers/blisters/sores suggestive of STI in vulva		
- Vulvitis		
- Any other lesion on vulva		
- Vaginal mass (polyp, myoma, etc.)		
- Ulcers/blisters/sores suggestive of STI in vagina		
- Vaginitis		
- Any other lesion on vaginal epithelium		
- Cervicitis		
- Any other lesion on cervical epithelium		
- Abnormal vaginal or cervical discharge/pus		
- Other, specify [additional categories to be made if needed]		
N women who underwent a bimanual exam		
Any abnormalities observed by physician during bimanual exam	N = xxx	N = xxx
If yes, which one(s) ¹ :	N = xxx	N = xxx
- Uterine mass		
- Adnexal mass on the right		
- Adnexal mass on the left		
- Uterine tenderness		
- Adnexal tenderness on the right		
- Adnexal tenderness on the left		
- Cervical motion tenderness		

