The following table describes, per possible infection, in what case treatment must be given per protocol. As mentioned before, the Rwandan guidelines include VDS algorithms that do not use risk scoring but use a pelvic examination to distinguish between mucopurulent cervical discharge and/or cervicitis (which is to be treated for CT/NG/TV) and non-muco-purulent vaginal discharge (which is to be treated for BV/TV/Candidiasis). We have decided to not take these algorithms into account.

Treatment given for:	WHO Syndromic Management	Rwandan Syndromic Management	WISH procedures	Gold standard procedures
СТ	Given with VDS and high risk / high local prevalence ¹ ; given with PID (after LAP) ²	Given with VDS and positive risk score ³ ; given with PID (after LAP) ² ; given as presumptive FSW treatment if asymptomatic ⁴	Positive for CT GeneXpert test performed after risk-scoring ⁵	Positive CT GeneXpert test (test performed on everyone)
NG	Given with VDS and high risk / high local prevalence ¹ ; given with PID (after LAP) ²	Given with VDS and positive risk score ³ ; given with PID (after LAP) ² ; given as presumptive FSW treatment if asymptomatic ⁴	Positive for NG after GeneXpert test performed after risk-scoring ⁵	Positive NG GeneXpert test (test performed on everyone)
TV	Given with VDS; covered with PID (after LAP) ²	Given with VDS no matter the risk score ³ ; covered with PID (after LAP) ² ; given as presumptive FSW treatment if asymptomatic ⁴	TV OSOM test	Positive qPCR test for Trichomonas vaginalis
UTI	NA	Treated based on reported symptoms	Positive urine dipstick test after reported symptoms ⁶	ND
BV	Given with VDS; covered with PID (after LAP) ²	Given with VDS and negative risk score ³ ; covered under VDS with positive risk score and PID (after LAP) ²	EcoCare pH swab (all pH ≥ 5.0 results treated)	Positive vaginal health qPCR DNA tool for BV ⁷

 ⁽As calculated by Log₁₀(*Lactobacillus* genus) – Log₁₀(*G. vaginalis* + *A. vaginae*). This DNA tool has a sensitivity and specificity comparable to the Nugent score. Further explained in the article by Jespers V, Crucitti T, [name] J et al. "A DNA tool for early detection of vaginal dysbiosis in African women." Res Microb 167.2 (2016): 133-41.

	on examination ⁸	or without notion of	algorithm after	
		recurrence) on	risk-scoring ⁹	
		examination		
Candidiasis	Given with VDS	Given with VDS and	Given with typical	Positive qPCR
	and typical signs	negative risk score ³	signs and	test for Candida

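### WISH CT/NG accuracy includes a speculum finding that the SAP itself expects to be rarely available; rows without it should be added

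*SAP*

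**What the plan says.** SAP 1.4 notes that both the WHO and the Rwandan guidelines hold two discharge algorithms, one with and one without an examination. It gives two reasons for leaving out the examination versions. The first is availability: "We believe that speculum examinations will rarely be available". The second is that the examination "cannot be reliably used to distinguish between different types of discharge". It concludes that "we will therefore only use the VDS algorithms in the absence of a speculum and bimanual examination when evaluating algorithm performances". The text before the treatment-by-infection table in SAP section 5 repeats this for the Rwandan pelvic-examination algorithms: "We have decided to not take these algorithms into account".

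For WISH, the fourth item of the CT/NG risk score in SAP 4.1 is "Abnormal cervicovaginal discharge during speculum exam and/or cervical motion/adnexal tenderness during bimanual exam". The scoring rule is "The risk score was positive if at least one of the four criteria was positive", and an examination that was not done counts as a negative answer. SAP 5.3 and 5.4 then set WHO, Rwandan and WISH procedures against the gold standard, with WISH scored on all four items throughout.

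Protocol 4.1 had described the score differently: "The questionnaire will be developed in the beginning of the project using the behavioural factors that were most strongly associated with these curable STIs".

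**The concern.** One premise, that speculum examination will seldom be available, is applied to the two comparators' discharge rules but not to the score that decides who gets a GeneXpert test under WISH. The score evaluated is thus an interview plus an examination, although Protocol 4.1 mentions only behavioural factors as its basis.

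This matters because risk scoring followed by testing, against syndromic management, is a stated secondary comparison. The SAP also looks ahead to clinics that would follow WISH procedures (end of SAP 7.4), and it makes work on an alternative score depend on how accurate this one proves (SAP 7.9). If those clinics lack a speculum, the WISH sensitivity reported is not the one that applies to them, and no planned row shows the one that does.

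**Working it through.** The documents state no accuracy figure for this point, so there is none to reproduce. The check compares definitions, then works out direction, then scale.

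**Definitions for CT/NG, side by side**
- WHO discharge branch (SAP 5.2): any reported discharge, with every such woman taken as high risk. No examination.
- Rwandan discharge branch (footnotes to SAP 5.2): reported discharge plus either a partner with urethritis or at least two of four interview items. No examination.
- PID branch, both guidelines: bimanual tenderness after reported lower abdominal pain. Examination kept.
- Rwandan presumptive branch: asymptomatic sex workers. No examination.
- WISH (SAP 4.1): pregnancy, sex exchanged in the past 12 months, new partner in the past three months, or the examination item. Any one suffices.
- Reference (SAP 4.2): GeneXpert on everyone, the assay WISH itself uses.

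The asymmetry is therefore specific: discharge seen on speculum counts for WISH and not for the comparators. Tenderness is used by all three, though the comparators require reported pain first.

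**Direction**

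Let N be all women with a result and D those who are GeneXpert-positive. Among D, let A be positive on at least one interview item and E positive on the examination item alone.
- Sensitivity as delivered = (A + E)/D.
- Sensitivity without the item = A/D.
- Difference = E/D, which cannot be negative.
- A woman counts as WISH-positive only if GeneXpert is positive, so false positives are zero either way. Specificity and PPV are 100% by construction.
- NPV = (N − D)/[(N − D) + (D − A − E)]. Setting E to zero lowers it or leaves it unchanged.

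**Scale (illustrative only)**

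Neither document gives E. For D, Protocol 4.3 expects 60 NG and 75 CT cases per 500 women: 60/500 = 12% and 75/500 = 15%. Applied to the 705 enrolled (SAP section 2):
- NG: 705 × 0.12 = 84.6. CT: 705 × 0.15 = 105.75.
- Women with either infection: 106 if the two overlap fully, 84.6 + 105.75 ≈ 190 if they do not overlap.
- One infected woman found by the item alone is worth 100/106 = 0.94 or 100/190 = 0.53 points of sensitivity.

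Loss of sensitivity when the item is removed, for assumed values of E/D:
- 0%: no loss.
- 2%: 2 points, from 2.1 to 3.8 women.
- 5%: 5 points, from 5.3 to 9.5 women.
- 10%: 10 points, from 10.6 to 19.0 women.

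For NPV, assume sensitivity of 75% without the item and E/D of 5%. At 15% prevalence, NPV falls from 0.85/(0.85 + 0.15 × 0.20) = 0.966 to 0.85/(0.85 + 0.15 × 0.25) = 0.958. At 27% (12% + 15%, no overlap) it falls from 0.931 to 0.915.

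The change of recruitment in September 2016 towards women with fewer positive scores (SAP section 2) means the protocol's prevalences may not hold, so D is itself an assumption.

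**The case against.** Much can fairly be said for the plan.

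- The SAP did not edit the guidelines; it chose a version that each of them contains. WISH is also properly evaluated as it was delivered.
- A reader might infer that speculum findings were dropped as unreliable in general and then relied on for WISH. The documents do not support that. The reliability objection concerns telling types of discharge apart, which the Rwandan examination version needs. WISH counts any abnormal discharge. Only the availability premise is in tension with the WISH item.
- A reader might infer that the comparators are held back by poorer information. That is not shown either. Under WHO, all reported discharge is already treated for CT/NG, so a speculum step could not raise sensitivity among those women and would mainly narrow treatment. The Rwandan examination version replaces the interview score, so its effect could go either way. The Rwandan rules also use partner urethritis, age and single status, which the WISH score lacks. Outside CT/NG, the comparators use examination for ulcers and for signs of candidiasis.
- The protocol is not purely behavioural on CT/NG: Appendix 14.3 links lower abdominal pain, after examination, to CT/NG testing.
- SAP 4.1 tabulates each score item, and SAP 7.9 would examine risk factors singly and together.

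These points narrow the concern to WISH's own CT/NG figures. They do not remove it. The table in SAP 4.1 counts women per item, not women positive on that item alone, and does not cross it with GeneXpert. The work in SAP 7.9 is conditional and left to a separate SAP.

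**Conclusion.** The point holds for WISH CT/NG sensitivity and NPV. Under the SAP's own availability premise, the planned values could overstate, and cannot understate, what WISH would achieve without speculum examination. The direction follows from the definitions, given that score-positive women carry the same GeneXpert result into the gold standard.

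The size is not derivable and may be near zero. Examinations were limited to women whose reported symptoms were relevant and at least moderate, and an examination not done scores as negative. The 2 to 10 points above are illustrations.

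A reader might construct a much larger effect. For example, if 15% of women were positive by examination alone, with 30% of them infected against 20% overall, the loss would be 0.15 × 0.30/0.20 = 22.5 points. None of those inputs is in the documents. They would also make women with no pregnancy, sex work or new partner more often infected than average, which is implausible.

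The 100% specificity of WISH for CT/NG comes from using GeneXpert as its own reference. That is a separate matter, and this item does not alter it.

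**What to change.** Keep the as-delivered WISH score as the main row in SAP 5.3 and 5.4. Add rows for CT/NG combined, CT and NG, giving sensitivity and NPV, scored:
- (a) on the three interview items only, to be read beside the no-examination discharge rows;
- (b) on the interview items plus bimanual tenderness but without speculum discharge, to be read beside the presumed-treatment rows, which include PID.

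Report how many women, and how many GeneXpert-positive women, were score-positive on the examination item alone. Limit conclusions about clinics without speculum examination to row (a). Row (b) should not replace the main row: it was not the algorithm delivered, and it still needs a bimanual examination.

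No new data are needed. GeneXpert results were planned for all participants, and the examination table in SAP 4.1 records "Abnormal vaginal or cervical discharge/pus" separately from the tenderness findings. The cost is a few extra rows, some SAP wording and possibly a less favourable WISH sensitivity.

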4.1 Monitoring and evaluation indicators

In this section, the *activities and outputs indicators* of the study will be reported. The *inputs and impacts indicators* will be reported in Section 7 (feasibility objectives).

Counselling:

All (705) women were offered counselling during the Main Visit. In addition, four women and two male partners received counseling at Additional Visits (these two men are not included in the table below). Women could choose their own counselling topics of interest with the exception of post-HIV test counselling: everyone who was tested for HIV was counselled in accordance with Rwandan VCT guidelines.

	MV	AV
	n (%)	n (%)
Concrete course alling norferment hu	IN = 705	IN = 4
General courseling performed by:		
- Nurse/counsellor		
- Physician		
Topics that were discussed during general counselling ¹ :		
– HIV basic facts		
– STIs basic facts		
– HIV & STI treatment		
– HIV & STI prevention		
- HIV & STIs: Condom use demonstration		
 BV and vaginal candidiasis basic facts 		

 BV and vaginal candidiasis treatment 	
 BV and vaginal candidiasis prevention 	
 UTIs: what it is, consequences if not treated, prevention 	
– Family planning	
 Domestic violence: including referrals 	
 Other, specify [categories to be made if needed: hepatitis, condylomata?] 	
HIV post-test counselling performed:	
- Nurse/counsellor	
- Physician	
Topics that were discussed during HIV post-test counselling:	
 Negative result for HIV test 	
 Positive or equivocal result for HIV test 	

Abbreviations: AV = additional visit; BV = bacterial vaginosis; MV = main visit; STI = sexually transmitted infection; UTI = urinary tract infection.

1. May total to more than 100% because women could choose multiple topics.

Risk scoring for CT/NG and syphilis:

All women were risk-scored for CT/NG and syphilis. Each of the two risk scores consisted of four questions based on the face-to-face interview and findings during speculum and bimanual examination (if applicable). GeneXpert CT/NG testing was only offered if the participant was positive for the CT/NG risk score and syphilis testing was only offered if the participant was positive for the syphilis risk score. However, a sample for GeneXpert testing was taken from all participants (a vaginal sample with the option of a urine sample if the participant refused vaginal sampling) so that we would have a CT/NG GeneXpert result for all participants at the end of the study. Participants who had a negative CT/NG risk-score but tested positive on the GeneXpert later on in the study were contacted for treatment at an Additional Visit.

CT/NG risk score	n (%) N = 705
Currently pregnant	
Exchanged sex for money or goods in the past 12 months	
New sex partner in the past three months	
Abnormal cervicovaginal discharge during speculum exam and/or cervical motion/adnexal tenderness during bimanual exam (if pelvic/bimanual not done, the answer was no)	
Final CT/NG risk score ¹ : - Positive	
- Negative	
Syphilis risk score	n (%)
Currently pregnant	
Exchanged sex for money or goods in the past 12 months	
New sex partner in the past three months	
Genital ulcers/blisters/sores visible during pelvic exam (if pelvic/bimanual not done, the	
answer was no)	
Final syphilis risk score ¹ : - Positive	
- Negative	

Abbreviations: CT = *Chlamydia trachomatis*; NG = *Neisseria gonorrhoeae*.

1. The risk score was positive if at least one of the four criteria was positive. If a speculum/bimanual examination was not done, the answer was no for that question.

Urogenital symptoms reported spontaneously and after structured questioning at Main Visits: During the face-to-face interview, participants were asked the following two questions in the order given:

- "Do you experience, or did you experience in the past 2 weeks, any urogenital symptoms?" We

will refer to these as *spontaneously reported symptoms*.

- "Do you experience, or did you experience in the past 2 weeks, any of the urogenital symptoms below?", followed by a list of symptoms that were read out loud to the participant. We will refer to these as *structurally reported symptoms*.

In the table below, we report the spontaneously and structurally reported symptoms, as well as the overlap in answers between the two questions. Each column contains n (% of 705).

Urogenital symptoms	Sponta-	Structural	Spontaneous but	Structural but
n (% of 705) in each column ¹	neous total	total	not structural	not spontaneous
Any reported				
Burning when passing urine				
Frequent urination/urge				
Blood in urine				
Genital burning				
Genital itching				
Postcoital/intermenstrual bleeding				
Pain during sex				
Lower abdominal pain				
Unusual VDS, curdlike				
Unusual VDS, offensive smell				
Unusual VDS, other ²				
Ulcers/blisters/sores genital/anal				
Warts genital/anal				
Swelling/bubo inguinal area				
Other ³				

Abbreviations: VDS = vaginal discharge syndrome

1. May total to more than 100% because the participant could report multiple symptoms.

2. These will be described in a footnote.

3. Additional categories may be added on to this list if certain other symptoms were mentioned frequently. Symptoms that were infrequently reported will be described in a footnote.

Other urogenital symptom-related questions	
	N = 705
Already receiving treatment for her current symptoms by another medical doctor or nurse	
Already took traditional medicine for her current symptoms	
At least one of the symptoms is ongoing	
At least one of participant's male partners has symptoms of urethritis (this question was	
asked because it is part of the Rwandan STI guidelines)	
- Yes	
- No	
- Does not know	
- NA	
At least one of participant's male partners has symptoms of swelling or tumefaction of the	
scrotum that did not start all of a sudden (this question was asked because it is part of the	
Rwandan STI guidelines)	
- Yes	
- No	
- Does not know	
- NA	

Abbreviations: IQR = interquartile range; NA = not applicable

Pelvic, bimanual and physical examinations performed at Main and Additional Visits: At the Main Visit, speculum and bimanual examinations were only performed if the participant reported relevant and moderate/severe urogenital symptoms. If she only had UTI-related symptoms (burning when passing urine, frequent urination or urge to urine, or blood in urine), a speculum and bimanual examination was not offered, and UTI testing and treatment were offered based on symptom-reporting. In the case of candidiasis-related symptoms (curdlike unusual vaginal discharge and genital itching), a speculum and bimanual examination was done at the discretion of the study physician; the protocol allowed the study physician to treat the participant based on the reported symptoms alone. If a pelvic and bimanual examination was performed, and no signs of vaginal candidiasis were seen, no treatment for vaginal candidiasis was given.

During Additional Visits, a pelvic and bimanual examinations were only performed if the participant had not had an examination at the Main Visit (for example, because she was menstruating), or if her symptoms had not resolved after having received treatment.

Speculum, bimanual, and physical examinations	MV n (%)	AV n (%)
	N = 705	N = 705
N women who underwent a speculum exam	•	
Reason for speculum exam ⁺ :	N = XXX	N = XXX
- To evaluate symptoms		
- At the participant's request		
- Another reason, specify [additional categories to be made if needed]	••	
Any abnormalities observed by physician during speculum exam	N = xxx	N = xxx
If yes, which one(s) ¹ :	N = xxx	N = xxx
- Enlarged/tender inguinal lymph nodes		
- Abnormal (genital) odour		
- Warts or condylomata (any location genitalia)		
- Ulcers/blisters/sores suggestive of STI in vulva		
- Vulvitis		
- Any other lesion on vulva		
- Vaginal mass (polyp, myoma, etc.)		
- Ulcers/blisters/sores suggestive of STI in vagina		
- Vaginitis		
- Any other lesion on vaginal epithelium		
- Cervicitis		
- Any other lesion on cervical epithelium		
- Abnormal vaginal or cervical discharge/pus		
- Other, specify [additional categories to be made if needed]		
N women who underwent a bimanual exam		
Any abnormalities observed by physician during bimanual exam	N = xxx	N = xxx
If yes, which one(s) ¹ :	N = xxx	N = xxx
- Uterine mass		
- Adnexal mass on the right		
- Adnexal mass on the left		
- Uterine tenderness		
- Adnexal tenderness on the right		
- Adnexal tenderness on the left		
- Cervical motion tenderness		

- Others, specify [additional categories to be made if needed]		
N women who underwent a physical exam by a physician		
Reason for physical exam n (%) ¹ :	N = xxx	N = xxx
 [Described in a footnote and/or categories to be made] 		
Abnormalities observed by physician during physical exam:	N = xxx	N = xxx
 [Described in a footnote and/or categories to be made] 		

Abbreviations: STI = sexually transmitted infection.

1. May total to more than 100% because there could have been multiple reasons or findings.

Services offered and opted out of, and results/referrals/treatments received at Main Visits: Participants were offered services as outlined in the background. Some services (such as HIV, BV, and TV testing) were offered to everyone. Others were only offered to a subset of participants: UTI testing was only offered in the case of reported UTI symptoms; CT/NG testing was only offered in the case of a positive CT/NG risk score; syphilis testing was only offered in the case of a positive syphilis risk score; and a speculum and bimanual examination was only offered in the case of relevant symptom reporting. Participants were subsequently asked if they wanted to opt-out of any service offered. The plan was to give participants their test results and referrals and/or treatments (if applicable) the same day, but this may not always have been possible. Also, in the case of GeneXpert CT/NG testing, participants were given the option to receive their results later on because the test takes 90 min. The table below summarises the services offered and accepted/declined at Main Visits, as well as whether results, referrals, and treatments were indeed delivered on the same day, at some other time, or not at all. *In this table, we will not yet take into account whether any mistakes were made by study staff along this pathway*.

Services	Offered	Declined	Reasons for	Sample taken	Received result	Received tx or
(n/705; %) ¹			declining ²		the same day	referral same day
HIV test ³			- Known HIV+: - Other: - NA - Missing	 EDTA blood: Fingerstick: NA: Missing: 	- Yes: - No, other time: - Not at all: - NA: - Missing:	- Yes: - No, other time: - Not at all: - NA: - Missing:
Pregnancy test ⁴			 Known pregnant: Other: NA Missing 	- Urine: - NA: - Missing:	- Yes: - No, other time: - Not at all: - NA: - Missing:	- Yes: - No, other time: - Not at all: - NA: - Missing:
